Approaches to increasing statistical power in randomized clinical trials generally focus on increasing sample size, but an alternative strategy is to introduce covariates that reduce within-subject error and thereby increase the precision of estimated between-group differences. The latter approach leads to a more sensitive significance test for the treatment effect¹⁵⁷. In the proposed R34, our sample size will be constrained by the number of youth who do not respond to CBT in the current R01 MH079943 study. Thus, we will increase the statistical power available by adjusting for relevant covariates measured at pre. Covariate adjustment for the pre score on each outcome measure will substantially increase statistical power¹⁵⁸. For example, if pre and post scores correlate at $r=.65$ (which seems reasonable based on the test-retest reliability estimates for our outcome measures and preliminary pre to post data from R01 MH079943), then power of 0.80 to detect a mean difference of $d=.50$ is available with a sample size of approximately 36 per group. Our projected sample size of 35 per group maps closely onto this estimate. To increase statistical power further, we will covary [pre attention bias scores] and examine other characteristics measured at pre (e.g., age, gender, diagnosis, R01 MH079943 condition, past treatment, current medication use, number of comorbid diagnoses) to determine whether they differ across conditions. If they vary across conditions, we will include them as covariates which will reduce the "noise" in the estimated treatment effect and thereby increase power. In general, the robust methods of analysis will be as powerful or more powerful than the least squares regression methods, so the power estimates above apply, conservatively, to the robust methods of analysis as well.

[For a test of moderation in Aim 3 that uses multiple regression, we will have power $> .80$ for a two tailed test ($\alpha=0.05$) of the interaction term based on an N of 70 for a medium effect size ($f^2=.15$).] For tests of mediation in Aim 3 that use bivariate or multiple regression, we will have power of about 0.80 for a two tailed test ($\alpha=0.05$) of a bivariate coefficient based on an N of 70 (i.e., pooling treatment & control groups) for an effect size that represents 10% explained variance, which seems reasonable for a mediator that is assumed to be relatively influential. For a multiple regression with two predictors, a two tailed test ($\alpha=0.05$), and an overall squared R of 0.20, the power is 0.80 to detect a coefficient that represents 10% unique explained variance. These levels of power seem reasonable given the preliminary nature of this facet of the research and the presumed role of the moderator and mediators based on substantive considerations.

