At each session, patients will be brought into a therapy room equipped with a table, chair, and computer. A 21-inch monitor and mouse will be on the table. Patients will sit facing the monitor and will be instructed to place their dominant hand on the mouse. Patients will be told that a probe (< or >) will appear on the screen and that their task is to push the left mouse button when < appears and to push the right mouse button when > appears. The importance of completing the task as quickly as possible without compromising accuracy will be emphasized. Patients then will complete 160 trials of the task. Trials will be presented in EPrime software. A centered fixation cross will appear first and will be followed immediately by two faces of the same actor against a white background, one above the other. One face will depict the actor emoting an angry expression and the other will depict the actor emoting no expression. Each face is 34mm in height and 47mm in width. After presentation of the faces for 500ms, a probe (< or >) will appear in the location of one of the faces. Patients will be instructed to indicate the type of probe (< or >) by pressing either the left or the right mouse button. The probe will remain on the screen until patients respond. After responding, the next trial will begin.

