In each session, patients will see 160 trials, 40 of which will include only neutral faces. The purpose of these 40 trials is to decrease the contingency ratio of neutral face: probe, which may reduce the chances that patients will identify the mechanism underlying the training paradigm. The remaining 120 trials will include one neutral face and one angry face. The faces to be used in the probe detection task were selected from a standardized set of emotional expressions used in previous ABMT trials^{41,44} with youth. The set includes 10 actors (5 male, all Caucasian) selected from the NimStim set of facial expressions¹²⁷ displaying angry or neutral expressions. We decided to use faces as task stimuli rather than words for three reasons. First, it avoids confounds between developmental aspects of emotional and linguistic processing. Second, research indicates that emotional faces generate larger and more consistent attention bias than threatening words^{17,128}. Third, face-based dot-probe tasks have been administered to non-human primates. Thus, the use of faces facilitates cross-species comparisons. [We decided to use these 10 faces because (1) they tap into threat-processing neural circuitry²³, (2) they are the identical stimuli used in the only published clinical trial of ABMT with referred anxious children⁴⁴, (3) they are being used in ongoing research in the UK, Netherlands, Germany, Israel, Brazil, and US and similar findings are emerging at all sites, and (4) there is no evidence of advantage for disorder specific stimuli faces³². Use of different faces, including faces of different emotions and faces of actors from different racial backgrounds, will be important for replication studies, but may introduce a confound in this first test of ABMT among CBT nonresponders.]

ABMT Task. In this task, the probe will replace the neutral face on 100% of trials. On 80% of trials, the location of the angry face will predict the location of the probe (i.e., in the location opposite the angry face). On these trials, angry face location (top or bottom) and actor will be fully counterbalanced. Probe type (< or >) will not be factorially counterbalanced but will appear with equal probability for angry-face location and actor. On the other 20% of the trials in this task, patients will see neutral-neutral face pairs.

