Placebo Control (PC) Task. The PC Task will be identical to the ABMT task except for the frequency with which the probe replaces the neutral face. 80% of trials include one neutral face and one angry face. On these trials, angry face location, probe location, and actor will be fully counterbalanced. Probe type will appear with equal probability for angry face location, probe location, and actor. The other 20% of trials include neutral-neutral face pairs. [The PC Task is an ideal control condition because it should be robust to differential expectancy effects, in contrast to other possible control conditions such as medication or behavior treatment.]

Task Administration. All sessions will be conducted by doctoral level graduate research assistants, who are blind to experimental condition and not involved in assessment procedures. Numeric codes representing experimental condition will be used to maintain the double blind (see Human Subjects). All research assistants will undergo thorough training in study procedures, which include (1) being trained in task protocol by [name], (2) administering practice sessions to [name], (3) administering one supervised session to a patient while being observed by [name] through the clinic's one way mirrors and (4) completing a session summary form jointly with [name] (see Measures). The ABMT and PC protocols are essentially contained on the computer software program. Graduate research assistants will be instructed to bring each patient to a therapy room and will start the software program. All instructions for the task appear on the computer screen and the investigative team's experience has been that youth readily understand the task. Additional details on task administration are provided in Human Subjects. This includes rationale for administering tasks in our clinic instead of having youth self-administer tasks at home.

Measures

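### Does the conflict between 120 + 40 trials and an 80%/20% split of the 160-trial session call for a change?

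*Combined protocol and SAP*

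**What the plan says.** The session is described in three places under Treatment Conditions, and once more under Measures.

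- **General Procedures** fixes the total, "Patients then will complete 160 trials of the task", and then gives counts: "In each session, patients will see 160 trials, 40 of which will include only neutral faces". The rest follow: "The remaining 120 trials will include one neutral face and one angry face". The neutral-only trials have a stated job: "The purpose of these 40 trials is to decrease the contingency ratio of neutral face: probe", so that patients are less likely to work out how the training operates.
- **ABMT Task** gives shares. The angry face predicts the probe location on 80% of trials, and "On the other 20% of the trials in this task, patients will see neutral-neutral face pairs".
- **Placebo Control (PC) Task** gives the same shares: "80% of trials include one neutral face and one angry face" and "The other 20% of trials include neutral-neutral face pairs". It also states how the two arms differ: "The PC Task will be identical to the ABMT task except for the frequency with which the probe replaces the neutral face".
- **Measures, III.a (Attention Bias to Threat)** says the assessment task matches the PC Task apart from a different set of faces. It scores the 120 angry-neutral trials and leaves out the 40 neutral-neutral ones.

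The Task Administration paragraph adds that the two protocols essentially reside in the computer program, which the research assistant starts.

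**The concern.** Counts and percentages that describe the same session should agree, and these do not. The conflict is in the current text, in complete sentences, and the percentages appear in two separate paragraphs.

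Three things could be at stake. First, the neutral-only trials are there to disguise the training contingency, so their number is part of the specification of the intervention and has some bearing on the blind. Second, the conflict carries over to the attention-bias measure: if the assessment task copies the PC Task and the PC Task is 80%/20% of 160, then 120 is not the number of trials available to score. That score is a candidate mediator under Aim 3, and its pre-treatment value is a planned covariate (Statistical Power). Third, someone replicating the trial from the document could not tell which mix was used.

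**Working it through.** **Inputs.** 160 trials per session, 120 angry-neutral and 40 neutral-neutral (General Procedures); 80% and 20% (ABMT Task, PC Task); eight sessions (General Procedures); 10 actors (General Procedures).

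**Counts to shares.** 120 + 40 = 160, so the counts agree with each other. 120/160 = 75% and 40/160 = 25%. The stated 80% and 20% are not reproduced.

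**Shares to counts.** 0.80 × 160 = 128 and 0.20 × 160 = 32.

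**Readings that might reconcile them.**
- *Rounding.* A quarter is not a rounded fifth.
- *Another session total.* 120/0.80 = 150 and 40/0.20 = 200. No single total satisfies both, and neither equals 160.
- *80% as a probe contingency, not a share of trials.* The ABMT sentence alone might allow this. But that paragraph assigns the remaining 20% to neutral-neutral pairs, and the PC paragraph states trial composition directly.
- *Different tasks.* The counts are given for sessions in both conditions, and the PC Task is said to match the ABMT task in everything but probe placement.

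The contradiction is therefore real.

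**Size.** 128 − 120 = 8 trials per session, and 8/160 = 5%. Over eight sessions, 8 × 120 = 960 against 8 × 128 = 1,024 angry-neutral trials, a difference of 64. This is a maximum, because treatment stops at six weeks even if fewer sessions have been completed.

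**Effect on the contrast between arms.** Both arms carry the same counts and the same shares. The arms differ in how often the probe replaces the neutral face, and the two trial mixes do not dispute that. An error in describing a feature common to both arms does not bias the difference between them.

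**Effect on the attention-bias score.** The rule keeps trials showing an angry-neutral pair and drops neutral-neutral trials. It is defined by trial type, so it can be applied whichever mix was programmed. If trial-level variance is constant and the error of a mean falls as 1/√n, the ratio of errors under 128 and 120 trials is √(120/128) = 0.968, a difference of about 3% before trials are excluded for errors or extreme latencies. As one of several covariates, a score measured 3% more or less precisely has no material effect on power.

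**Consistency with the counterbalancing text.** Full counterbalancing is stated over angry-face location and actor for ABMT (2 × 10 = 20 cells), and over angry-face location, probe location and actor for PC (2 × 2 × 10 = 40 cells). Within a session, 120/20 = 6 and 120/40 = 3 are whole numbers; 128/20 = 6.4 and 128/40 = 3.2 are not. This is an observation on the text only. It does not establish which mix was programmed or intended.

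**The case for a change.** The strongest case for asking for a change is that the trial mix is part of the intervention. The neutral-only trials serve the masking of the training, the document states their number in two incompatible ways, and the conflict reaches a measurement rule. The remedy would be cheap: look at the task script and correct a sentence.

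Part of this stands. The text does contradict itself, no charitable reading removes it, and a reader who wants to replicate the task must look at the program. The conflict in the attention-bias section also exists, although it is the same slip seen a second time and adds no weight.

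The step from there to a change in the plan does not stand. Nobody has to choose between the statements when running a session, because the assistants start a finished program. The share of neutral-only trials is 25% under one description and 20% under the other, and it applies equally to both arms. The plan also asks youth and parents at follow-up which condition they believed the youth was in, so the blind is checked whatever the mix. No passage links any outcome to a difference of 8 trials. The Human Subjects section is cited for further detail on task administration but is not among the supplied text. It might state the mix, but it could not remove the contradiction in what is visible.

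**Conclusion.** This is a clerical inconsistency, and no change to the plan follows. Its size is 8 of 160 trials per session (5%) and at most 64 trials per patient. It does not bias the ABMT versus PC comparison on the PARS or on either SCARED version, and the alpha level and planned sample size do not depend on it. The only route to power is through the precision of one covariate, where the trial-sampling error changes by about 3%, which is negligible.

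The conclusion rests on three assumptions: that both arms were programmed with the same mix, as the PC Task paragraph states; that scoring follows trial type, as the attention-bias section describes; and that trial-level variance is roughly constant, for the 3% figure. The documents show an inconsistent description and give no sign of an error in delivery. The statements do need to agree with each other and with the program when the task is reported, and no view is taken here on which mix is correct. Correcting the sentence would alter neither the conduct of the trial nor the conclusions it can support.

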Threat Related Attention Bias in Anxious Youth and Adults. There is substantial convergent evidence of threat related attention bias in anxiety from behavioral and neuroscience research⁶⁻⁸. A common paradigm for assessing threat related attention bias is the visual probe-detection task. In the most widely used form of the task, a pair of threatening and neutral stimuli (e.g., facial expressions) is presented simultaneously and then followed immediately by a visual probe (e.g., a dot). The probe replaces the threatening stimulus on some trials and the neutral stimulus on others. An individual’s difference in average response times when identifying the location of the probe following threatening stimuli versus neutral stimuli provides an index of attention bias.

Anxious individuals typically display faster response times on trials in which the probe replaces the threatening stimuli, which reflects an attention bias toward threat⁷. This pattern has been replicated among children⁹⁻¹⁵, adolescents¹⁶, and adults¹⁷⁻¹⁹, including youth and adult patients with Social Phobia (SOP)^{12,14,18} and Generalized Anxiety Disorder (GAD)^{12-14,17,20}, youth patients with Separation Anxiety Disorder (SAD)^{12,14}, and youth and adults with subclinical anxiety symptoms^{9,16,21}. Cortical-subcortical circuitry findings from brain imaging studies correspond to these behavioral findings: Researchers have evoked an amygdala–ventrolateral prefrontal cortex (LPFC) circuit involved in attention to threat^{16,22-27}. The amygdala is believed to facilitate vigilance through immediate, reflexive threat processing that occurs below awareness; the LPFC is believed to facilitate later strategic processes related to emotion regulation^{22,24,25,28,29}. These findings suggest LPFC activation compensates for amygdala hyperactivation.

Anxiety is unique relative to other psychiatry symptoms in that there is marked cross-species conservation of brain-behavior associations. Specifically, across a range of mammalian species, similar changes in neural circuitry engagement and information processing occur when an organism confronts a threat³⁰. This is also true for referred and nonreferred children, adolescents, and adults³¹, suggesting developmental continuity in the neural circuitry underlying response to threat.

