Guided by the findings that attention bias to threat predicts CBT anxiety nonresponse⁴⁹ and the role of attention control as a potential moderator⁵⁵⁻⁵⁸, we asked [name] to join our investigative team as a consultant. We are grateful he agreed, as he has studied and written extensively about the interaction between attention control and attention bias^{55,56,58}. [name] worked with us to refine our model for this resubmission, which now draws more sharply the conceptual connections between attention bias to threat and CBT nonresponse depending on youths' levels of attention control (see Figure 1).

As shown in Figure 1, our model proposes the bottom up process of attention bias to threat as likely to interfere with youths' ability to benefit from CBT when they are unable to strategically modulate attention bias through attention control. That is, amygdala based attention bias to threat is posited to have a negative impact on CBT response in the absence of LPFC based compensation strategies. We recognize Figure 1 represents just

[figure not shown]

Figure 1. Theoretical model of the relations between attention bias, attention control, and CBT nonresponse.

one of multiple potential paths to CBT anxiety nonresponse. We elaborate on this point in the subsequent section, "Why Modify Attention Bias in this R34 rather than Other Variables?"

Also in response to previous critiques, we further refined our theoretical working model about how ABMT may lead to anxiety symptom reduction among CBT nonresponders. As shown in Figure 2, ABMT directly reduces attention bias to threatening stimuli^{32,44}. Attention bias may have a direct effect and an indirect effect through interpretation bias on anxiety symptoms^{61,62}. These effects are expected to be moderated by attention control: Youth with lower attention control may benefit more from an intervention that targets a bottom up process such as attention bias to threat than youth with higher attention control^{53,55}.

The model may be more complex than depicted in Figure 2

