b. Screen for Child Anxiety Related Emotional Disorders – Parent Version (SCARED-P)^{132,133}. Parent ratings represent important additional outcomes in all youth anxiety randomized trials^{136,137}. There is scant controlled parent data following youth participation in ABMT. We will address this gap in the literature by assessing outcome from parents' perspectives using the parent version of the SCARED. The reliability and validity of the SCARED-P have been demonstrated repeatedly and mirror those of the SCARED-C^{132,133,135}.

III. Potential Mediators and Moderator

We will assess each of the potential mediators and the hypothesized moderator shown in Figure 2 at each assessment session (Figure 3) to inform decisions about our future R01.

a. Attention Bias to Threat. As in prior research^{36,41}, attention bias to threat will be assessed with a probe-detection task identical to the one used in the PC Task, with the exception that unique faces will appear in this task (i.e., a different set of 10 faces will be used). Inaccurate responses when the probe appears on one side of the screen but patients select the other side will be excluded, as will trials with response latencies <50ms and >1200ms. Similar criteria have led to the exclusion of <5% of trials among adults³⁷ and children^{36,42}.

Attention bias scores will be calculated by subtracting the mean response time on trials in which the probe appears at the neutral face location from the mean response time on trials in which the probe appears at the angry face location. Only the 120 trials that present angry-neutral face pairs will be used to calculate scores (the 40 neutral-neutral trials will be excluded). Positive values reflect an attention bias towards angry faces.

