Aim 2: Examine whether ABMT, as compared to PC Task, leads to significantly lower levels of anxiety at an eight week FU. This aim represents a test of the maintenance of ABMT effects over eight weeks. The analysis will focus on the between-groups contrast between patients in the ABMT condition (n=35) and patients in the PC Task condition (n=35). Patients’ mean scores on the FU measures will be contrasted using a single degree of freedom contrast as a function of condition (ABMT, PC Task) in a between-groups design with the pre scores as a covariate. The single degree of freedom contrast focuses on the comparison of adjusted means at FU. Of interest is whether the contrast between conditions is statistically significant for IE ratings of youth anxiety severity (PARS; **Hypothesis 2a**), parent ratings on youth’s anxiety symptoms (SCARED-P; **Hypothesis 2b**), and youth self ratings on anxiety symptoms (SCARED-C; **Hypothesis 2c**). Significantly lower scores in the ABMT condition as compared to the PC Task would demonstrate that ABMT produces reductions in anxiety at least eight weeks after treatment has ended. The robust counterparts of these contrasts are those described for Aim 1¹⁴⁹.

Aim 3: Gain perspective on the viability of variables as potential mediators and moderator of ABMT (Figure 2). This aim represents an exploratory aspect of this R34 application that will lay the groundwork for a larger R01, which may include testing of the mediators and moderator of ABMT’s anxiety reduction effect. As

Aim	Contrast	Outcomes
Aim 1: Efficacy	ABMT vs. PC Task at Posttreatment	PARS, SCARED-C/P
Aim 2: Maintenance	ABMT vs. PC Task at Follow up	PARS, SCARED-C/P
Aim 3: Potential Moderator & Mediators	1. ABMT vs. PC Task at Posttreatment (immediate effect) 2. ABMT vs. PC Task at Follow up (maintenance effect)	Attention Bias & Interpretation Bias (mediators), Attention Control (moderator)

Table 2. Planned Analyses.

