described earlier, reduction in attention bias toward threat and threat-related interpretation bias represent proposed potential mediators of ABMT^{61,62}, and [attention control is expected to moderate the effects of ABMT on anxiety symptom severity⁵⁵⁻⁵⁸.] Although it is premature given the current state of the field to pursue tests for the full moderated mediation chain depicted in Figure 2 in this R34, it is reasonable to use the data to gain some perspectives on the viability of proposed moderator and mediators so as to inform decisions to pursue them in the larger R01. [The traditional moderation analysis relies on least squares regression with a focus on the statistical significance of the product term of the independent variable (condition) and the moderator (attention control) in predicting the dependent variable (anxiety symptom severity)¹⁵³. In this R34 pilot study, and given our desire to balance risk of Type I and Type II errors, we will only test attention control as a moderator of the association between condition and anxiety symptom severity. The other two moderation effects depicted in Figure 2 will be tested in a larger R01 if initial support for the primary moderation hypothesis is obtained in this R34.

Mediation paths (Figure 2) can be explored in several ways. One strategy tests the joint significance of the path from the treatment to the mediator and the path from the mediator to the outcome. This follows the logic of the joint significance test of mediation by MacKinnon¹⁵⁴, but we will use the newer, more powerful partial posterior p value method by Biesanz¹⁵⁵. This latter approach fares better than the asymmetric confidence interval approach for testing statistical significance¹⁵⁵. A robust analog to the joint significance test will use Theil-Senn regression as applied to the target paths and then apply the logic of MacKinnon's joint significance to them. The magnitude of each indirect effect can be subjected to decompositional analyses through multiplicative and summation rules for mediation and the proportion of the total effect that each mediator accounts for can be documented (using the algorithms from the Mplus computer package¹⁵⁶). Confidence intervals around these decomposed effects can be formed using percentile bootstrapping, which perform better than bias-corrected bootstraps in the context of such mediation analysis – see Biesanz¹⁵⁵.]

Statistical Power

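### The attention-bias formula gives a negative score for bias toward threat, but the plan reads positive scores as bias toward threat

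*Combined protocol and SAP*

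**What the plan says.** Under Measures, III. Potential Mediators and Moderator, a. Attention Bias to Threat, the score is obtained by "subtracting the mean response time on trials in which the probe appears at the neutral face location from the mean response time" on trials with the probe at the angry face. Only the 120 angry-neutral trials count. The paragraph ends with the reading of the sign: "Positive values reflect an attention bias towards angry faces".

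The behavioural meaning of bias is given in Significance, Threat Related Attention Bias in Anxious Youth and Adults. Anxious individuals typically show "faster response times on trials in which the probe replaces the threatening stimuli, which reflects an attention bias toward threat". That section describes the index as a difference in response times but does not give the order of subtraction, so the Measures paragraph is the only scoring rule in the document.

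The score is used in three ways:

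- **Working model.** The text on Figure 2 says "ABMT directly reduces attention bias to threatening stimuli". It gives attention bias a direct effect on anxiety and an indirect one through interpretation bias.
- **Aim 3 (Data Analysis).** Here "reduction in attention bias toward threat and threat-related interpretation bias represent proposed potential mediators of ABMT", and the results are to be used "so as to inform decisions to pursue them in the larger R01".
- **Statistical Power.** The pre-treatment bias score is a covariate in the outcome analyses.

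**The concern.** The scoring rule and its interpretation cannot both hold. A child whose attention is drawn to angry faces responds faster when the probe appears there, and subtracting the larger neutral-trial mean from the smaller angry-trial mean gives a negative number. The plan would read that child as biased away from threat.

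Direction is what gives this variable its scientific meaning. ABMT is expected to lower bias, and lower bias is expected to go with lower anxiety. If scored as written and read as stated, successful training would appear to increase bias toward threat, and higher bias would appear to go with less anxiety. Both would count against the model that Aim 3 is meant to assess. Baseline bias would also be misread. That matters because Research Overview and Future Plans proposes baseline attention bias as one variable for deciding, in the later R01, which patients receive which treatment.

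The p values do not change under a reversal, so significance testing alone would not reveal the error.

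The same paragraph has a minor wording slip. It treats a response as inaccurate when the child picks the wrong side of the screen. Under General Procedures the faces are stacked vertically and the mouse button codes the probe type (< or >), so no side is selected.

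**Working it through.** **Inputs from the plan**

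- Score as written (Measures, III.a): S = RT(angry) − RT(neutral), where the label gives the probe location.
- Stated reading (Measures, III.a): S > 0 means bias toward angry faces.
- Definition of bias toward threat (Significance): RT(angry) < RT(neutral).
- Sample and schedule: 70 youth, with the mediators measured at pre, post and FU.

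**Step 1: sign of the score.** If RT(angry) < RT(neutral), then S = RT(angry) − RT(neutral) < 0. The stated reading requires S > 0. The conflict does not depend on the size of the response times. An illustration with assumed values (the plan gives no response times):

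| RT(angry), ms | RT(neutral), ms | Meaning per Significance | As written | Reversed order |
|---|---|---|---|---|
| 480 | 500 | toward threat | 480 − 500 = −20 | 500 − 480 = +20 |
| 500 | 500 | none | 0 | 0 |
| 520 | 500 | away from threat | 520 − 500 = +20 | 500 − 520 = −20 |

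Only the reversed order matches the stated reading.

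**Step 2: number of scores.** At most 70 × 3 = 210; attrition would reduce this.

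**Step 3: effect on the analyses.** Let M be the score in the intended direction, so the score as written is −M.

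- Condition to bias: the coefficient a becomes −a.
- Bias to anxiety: the coefficient b becomes −b. A Theil-Sen slope also changes sign, because every pairwise slope does.
- Bias to interpretation bias: this coefficient also changes sign. The plan commits to all mediation paths in Figure 2, so at least three paths involve the score.
- Product indirect effect through bias: (−a)(−b) = ab, unchanged. The chain through interpretation bias also contains two reversed coefficients, so its product is unchanged.
- Two-tailed p values: unchanged, since each estimate changes sign while its standard error does not.
- Treatment contrast on PARS or SCARED with pre-bias as a linear covariate: unchanged. Only the covariate's own coefficient changes sign.

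**Step 4: numerical illustration.** One simulated trial had 35 per group and assumed, in the intended direction, a baseline bias with mean 20 ms and SD 40 ms, an ABMT effect of −20 ms, a PARS slope of 0.04 per ms and a pre-post PARS slope of 0.65.

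| Quantity | Intended sign | Sign as written |
|---|---|---|
| Sample mean baseline bias, ms | +11.3 | −11.3 |
| Condition to bias, ms | −20.26 (p = 0.0476) | +20.26 (p = 0.0476) |
| Bias to PARS, points per ms | +0.0378 (p < 0.001) | −0.0378 (p < 0.001) |
| Product of the two | −0.766 | −0.766 |
| PARS contrast, pre-bias as covariate | −0.724 (p = 0.342) | −0.724 (p = 0.342) |

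These values depend on the assumed inputs and do not predict the trial's results. They only show the algebra of Step 3 at work.

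**The case against.** The strongest reply is that the intended meaning is clear. The Significance section and the stated reading of positive values agree, and only the order of two terms in one sentence conflicts. The team may well have scored the task correctly, and the document does not show otherwise. Of the score's own mean, a baseline average pointing away from threat would look odd enough that someone might notice. Aim 3 is also labelled: "This aim represents an exploratory aspect of this R34 application". The formal mediation evidence (joint significance, partial posterior p values and the size of the indirect effect) would be the same either way, so the harm to R01 decisions should not be overstated.

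Much of this stands. It limits the consequence to the direction of baseline bias, of its change, and of the individual paths. It does not remove the contradiction. This sentence is the only scoring rule in the plan, and an analyst who follows it gets the reversed sign. Detection by eye is possible but not assured. The paths are also meant to be read individually, since the model predicts a direction for each.

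The contradiction could also be removed by keeping the formula and calling negative values bias toward threat. That would be consistent, but a reduction in bias would then mean a rising score, which sits badly with the language used for Figure 2 and Aim 3.

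**Conclusion.** The concern holds. As written, every non-zero attention-bias score has the opposite sign to its stated meaning; this follows from two passages of the plan and needs no assumption about response times. If the formula was implemented literally and read as stated, up to 210 scores would be misread, a true reduction in bias would be reported as an increase, and at least three individual mediation paths would change direction.

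Whether this happens depends on a scoring script that the document does not show. The primary and secondary anxiety contrasts, the adjustment for pre-treatment bias in a linear model, the two-tailed p values and the indirect effects are not affected. The point should be fixed before Aim 3 is analysed, but it does not threaten the main efficacy result.

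**What to change.** In Measures, III.a, define the score as mean RT with the probe at the neutral location minus mean RT with the probe at the angry location, on angry-neutral trials, and keep the existing statement about positive values. Check the scoring script against this definition, for example by passing through it one record with known faster responses at the angry face and confirming a positive result.

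As a minor correction in the same paragraph, define an inaccurate trial as one where the button pressed does not match the probe type (< or >).

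The cost is two sentences of text and a script check. No new data are needed. If scores have already been produced with the order as written, multiplying them by −1 corrects them.
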